12.0 CRITERIA FOR THERAPEUTIC RESPONSE/OUTCOME ASSESSMENT

- 12.1 At 16 weeks (completion of Doxil® treatment) and after 16 weeks of Targretin® treatment: CT scans of chest, abdomen and pelvis for TNM stage IV patients who had positive findings prior to treatment.

**Memorial Sloan-Kettering Cancer Center
IRB Protocol**

IRB#: 05-098 A(6)

- 12.2 History and physical examination including skin assessment
- 12.3 Karnofsky performance status.
- 12.4 CBC with Sézary cell count and/or flow cytometry in patients with Sézary syndrome.
- 12.5 Assessment of response status and any residual toxicity will be performed 4 weeks after completion of treatment.
- 12.6 Biopsy of residual lesions 4 weeks after the completion of treatment if clinical complete remission is suspected.
- 12.7 Dermatologic evaluation of response

Dermatologic responses will be determined by the Severity-Weighted Assessment Tool (SWAT), a standardized approach to measuring the extent and severity of overall skin disease in patients with CTCL. It will be briefly described and full details are provided in an appendix. The purpose of this description is to optimize intra-observer objectivity and to minimize the potential for intra-observer and inter-observer variability in the measurement of overall skin disease. Only physicians who received training will be permitted to conduct SWAT assessments during the clinical study. It is essential that physicians adhere as closely as possible to the prescribed procedures so as to reduce measurement error and variability. All efficacy assessments should be performed by the same physician for each patient whenever possible. Physicians will be instructed not to examine previous SWAT assessments and full body photographs prior to conducting the current SWAT assessment.

1. Total Body Surface Area (TBSA) Involvement by Skin Disease

The body is divided into 12 regions with pre-assigned %TBSA based on the burn literature. The extent of skin disease in each region is quantified by using the patient's palm to measure the %TBSA involvement within region:
Patient's palm with 4 fingers (excluding the thumb) is 1% of TBSA
Patient's palm without fingers is 0.5% of TBSA.

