Responses will be determined by the criteria described in the table below. Progression of disease while on treatment should be confirmed by a second assessment 1-4 weeks later so that patients who experience a temporary flare of disease due to skin infection or other intercurrent illnesses are not removed from the study prematurely.

Assessment	Description	Status
Completely clear	No evidence of disease; 100% improvement	CCR
Marked Improvement	Greater than or equal to 50% decrease in skin scores compared to baseline and improvement is maintained for 4 weeks	PR
Slight Improvement	Less than 50% decrease in skin scores compared to baseline	SD
Worse	$\geq 25\%$ increase in skin scores compared to baseline while the patient is actively taking the study drug or $\geq 50\%$ increase in the sum of the products of the greatest diameters of pathologically positive lymph nodes (should be documented by biopsy) compared to baseline while the patient is actively taking the study drug.	PD

Assessment of Overall Skin Disease

Pruritus Relief (Appendix 1)

The intensity of pruritus will be evaluated by the patient at baseline, at the week 16 (end of treatment with Doxil®) and week 32 (after 16 weeks of treatment with Targretin®) using a 1-10 point scale, where 0 is no pruritus and 10 is the worst imaginable pruritus. A 3-point decrease in pruritus intensity confirmed by a second assessment at least 4 weeks later without an increase in the use of anti-pruritic medications is considered clinically significant in those whose pruritus score is ≥ 3 on the 0-10 point scale at baseline.

4. As a secondary goal, index lesion severity will be evaluated by a modified Composite Assessment Scale (Appendix 2). These are measurements of skin disease that have been employed and validated in the phase II-III studies of Targretin® and in the current MSKCC trial of Targretin® of Intron-A® (IRB #01-128) in CTCL. Up to 4 index skin lesions will be chosen from representative patch, plaque and tumor lesions, and erythrodermic lesions. For erythrodermic patients, a 10x10 cm. area, easily identified by anatomic landmarks will be chosen and assessed by the same scale. These index lesions will be photographed and assessed at the same time as the SWAT assessment.

In the Phase II-III studies of Targretin capsules in CTCL, the Composite Assessment (CA) of Index Lesion Disease Severity was based on a core element of the summation of index lesion

**Memorial Sloan-Kettering Cancer Center
IRB Protocol**

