13.0 CRITERIA FOR REMOVAL FROM STUDY

If at anytime the patient develops progressive disease he/she will be taken off study and referred for alternative therapy.

If at anytime the patient develops unacceptable toxicity he/she will be removed from study. If

at anytime the patient is found to be ineligible for the protocol as designated in the section on Criteria for Patient/Subject Eligibility (i.e., a change in diagnosis), the patient will be removed from the study.

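### As written, the Section 12.7 table makes a stage IV or Sézary patient with worsening visceral or blood disease a PR, and gives no precedence when nodal PD and PR coincide

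*Combined protocol and SAP*

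**What the plan says.** Section 12.7 introduces its table with "Responses will be determined by the criteria described in the table below". The rows are:

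- CCR: "No evidence of disease; 100% improvement".
- PR: "Greater than or equal to 50% decrease in skin scores compared to baseline and improvement is maintained for 4 weeks".
- SD: a fall in skin score of under 50%.
- PD: a rise of at least 25%, worded as "increase in skin scores compared to baseline while the patient is actively taking the study drug", or a rise of at least 50% in the summed products of pathologically positive nodes, also only while on study drug.

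The subsection is titled "Dermatologic evaluation of response". Of the skin tool (SWAT) it says "It will be briefly described and full details are provided in an appendix"; Appendices 1 to 4 as supplied do not contain those details. Section 1.0 refers to SWAT as used in two other institutional protocols. It lists CT for stage IV and Sézary counts among the evaluations, but sets no threshold for either.

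Section 6.1 admits stages IB to IV and mentions Sézary syndrome by name. Section 12.1 repeats CT in some stage IV patients, and Section 12.4 calls for "CBC with Sézary cell count and/or flow cytometry in patients with Sézary syndrome". Section 13.0, like Section 5.0, adds: "If at anytime the patient develops progressive disease he/she will be taken off study and referred for alternative therapy". Neither defines progressive disease. The secondary endpoint is the CR+PR rate (Sections 2.0 and 14.0); the primary endpoint is PFS at 12 months (Section 14.0).

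**The concern.** CTCL at stage IV or with Sézary syndrome is not confined to skin. The plan collects CT and blood data on these patients at both response assessments, yet no row of the table uses visceral findings, Sézary count or flow cytometry. A patient can thus be improving in skin, worsening elsewhere, and still satisfy the written definition of a responder.

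At stake is mainly what the CR+PR rate means. Section 5.0 reports that the earlier Targretin studies granted PR only if there was no worsening and nothing new in the form of skin tumours or disease outside the skin. Without that condition, the response rate here is not like for like with theirs. For PFS, the risk is that sites apply different private thresholds for calling extracutaneous progression in an open-label, multi-center trial.

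**Working it through.** **Step 1. Apply the rows.** Take three patients, each with a skin score down at least 50% for 4 weeks but not cleared.

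| Patient | CCR | PR | SD | PD | Result |
|---|---|---|---|---|---|
| A: nodes stable; new visceral disease or rising Sézary count | no | yes | no | no | PR |
| B: positive nodes up 50% or more, on drug | no | yes | no | yes | PR and PD, no precedence |
| C: new positive node, baseline nodal sum zero | no | yes | no | undefined | PR |

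For C, the percentage change is (new sum − 0)/0, which has no value. CCR is less exposed, because its wording can be read as covering every disease site.

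**Step 2. Look for another rule.** Section 1.0 lists tests without thresholds. Section 13.0 uses the term progressive disease without defining it. Section 10.6 mentions signs or symptoms of progression, but only as the point at which follow-up visits end. None of these changes the results in Step 1.

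**Step 3. Size for the response rate.** Taking all 37 patients as the denominator, each patient like A adds 1/37 = 0.027, or 2.7 percentage points. The number of such patients cannot be derived, since the documents give no stage mix and no rate of progression confined to viscera or blood.

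**Step 4. The PFS rule.** Section 14.0 requires at least 24 of 37 patients progression-free at one year. A 12-month median implies a 12-month rate of 50%; the target is 70%. With X binomial (37, p):

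- P(X ≥ 24 | p = 0.50) = 0.0494, against the stated 0.05.
- P(X ≥ 24 | p = 0.70) = 0.8071, against the stated 0.80.

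The design reproduces as a one-sided test. Turning the gap in the table into an effect on these figures would need the number of missed events, which the documents do not give.

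**Step 5. Who is rescanned.**

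| Place | Repeat CT for |
|---|---|
| 10.2 and 10.6 | stage IV with baseline lymphadenopathy |
| 12.1 | stage IV with positive findings before treatment |
| Appendix 3 | all stage IV |

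Under 10.2 and 10.6, a stage IV patient with visceral disease but no enlarged nodes is not rescanned, so visceral worsening could go unseen as well as unclassified.

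**The case against.** The strongest reply is that this is a skin table. Its subsection title and its label as an assessment of overall skin disease say so, and Section 12 lists CT, examination and blood tests as separate items. An overall rule may have been intended, and may exist in the two protocols named in Section 1.0 or in the missing SWAT appendix. What stands is that the claim can only be about the supplied text. But the PD row has a nodal limb, so the table already reaches beyond skin. If it were skin-only, CR+PR and PFS would have no overall definition at all, and the remedy would be the same.

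The second reply is that Section 13.0 removes a progressing patient at any time, while PR must be held for 4 weeks. That does narrow the route to a false PR: an investigator must see the worsening and not call it progression, or not see it. It does not close the route, because nothing tells investigators when visceral or blood change counts.

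A reader might go further and infer that the primary test's type I error is inflated. Suppose the true rate is 50% and a share f of progressors is never called; the apparent rate is then 0.50 + 0.50f. The chance of reaching 24 would be 0.0494, 0.0891, 0.1488 and 0.335 for f = 0, 5%, 10% and 20%. One missed patient lowers the effective bar to 23, with P(X ≥ 23 | p = 0.50) = 0.0939. The documents support none of these values of f, nor even one missed event. Such a patient must progress only in viscera or blood before month 12, show no qualifying skin or nodal progression by then, and not be called by the investigator. These figures are illustrations and should carry no weight.

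**Conclusion.** The point holds for the text as supplied. The stated rule, applied literally, classes some patients with extracutaneous worsening as PR, and it leaves PR with nodal growth unresolved. This is a rule that gives a wrong answer, and the protocol should correct it.

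The main exposure is the PR component of CR+PR, at 2.7 points per patient and with an unknown number of patients. The exposure of 12-month PFS to visceral or blood progression is real but smaller, since investigators may call it under Section 13.0, and its size cannot be computed. Confidence is medium. The conclusion assumes that no overall response rule exists in the unseen SWAT appendix or in the protocols that Section 1.0 mentions.

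**What to change.** **Response.** In Section 12.7, require no new or worsening nodal, visceral or blood disease for PR and SD, following the precedent described in Section 5.0. State that PD overrides PR.

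**PFS events.** Count each of the following:

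- skin or nodal progression, whether or not the patient is still on study drug;
- a new biopsy-positive node;
- new or enlarging visceral disease on CT;
- blood progression by a Sézary count or flow threshold that the investigators fix in advance;
- death.

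**Imaging.** Change Sections 10.2 and 10.6 at least to the 12.1 rule of any positive baseline finding. Do not narrow Appendix 3: its scans of all stage IV patients are the ones that could show new visceral disease.

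**Cost.** The change is wording plus one clinical decision on the blood threshold. It adds no CT beyond the Appendix 3 schedule and does not change the sample size. PR and PFS figures may be slightly less favourable. Scheduled CT and blood assessments still end at about week 32, so later extracutaneous progression would rest on the visits at least every 3 months.

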10.0 EVALUATION DURING TREATMENT/INTERVENTION

10.1 Treatment visits every 2 weeks for Doxil® administration for 16 weeks. At each visit: history, physical exam, KPS, toxicity assessment, CBC, platelet count.

10.2 Tumor assessment within 2 weeks following the last dose of Doxil®, optimally between 7 and 14 days. For patients with stage IV disease (TNM) with baseline lymphadenopathy on CT scans of chest, abdomen and pelvis: repeat CT scans of chest, abdomen and pelvis. Patients with Sezary syndrome will have Sézary cell count and/or flow cytometry. Patients who have a CCR should have a biopsy to document a pathological CR. Two item self-reported pruritus questionnaire will be administered at time of tumor assessment. The details for tumor assessments at 16 and 32 weeks are described in Section 12.0 and in the Table in Appendix 3.

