10.3 Cardiac Safety Monitoring

All patients will be monitored for a decrease in LVEF based on the criteria below: Baseline Left Ventricular Ejection Fraction (LVEF) determinations will be performed on all patients prior to enrollment in the trial. Patients will not be enrolled if LVEF <50%. If during treatment the LVEF falls to $\leq 45\%$, or the ejection fraction (LVEF) falls by 20% from the baseline level, Doxil® will be discontinued. The investigator

**Memorial Sloan-Kettering Cancer Center
IRB Protocol**

IRB#: 05-098 A(6)

may verify the LVEF from a MUGA by obtaining an ECHO with cardiac consultation. If there is no evidence of cardiac damage determined by ECHO the patient may continue on treatment.

MUGA or ECHO (LVEF) Schedule for all patients:

- f* Cumulative anthracycline dose of $< 350\text{mg}/\text{m}^2$: physicians discretion
- f* Cumulative anthracycline dose of $\geq 350\text{mg}/\text{m}^2$: every two cycles

10.4 Within 2 weeks of tumor assessment: history, physical exam, KPS, CBC, platelet count, total bilirubin, SGOT (AST), SGPT (ALT), creatinine, uric acid, fasting triglycerides and cholesterol, T4, TSH.

10.5 Within 2 weeks after tumor assessment begin oral Targretin® for 16 weeks.

10.6 Followup visits: at 2 weeks, 4 weeks, 8 weeks, 12 weeks, 16 weeks: history, physical examination, KPS, CBC, platelet count, total bilirubin, SGOT (AST), SGPT (ALT), creatinine, uric acid, fasting triglycerides and cholesterol, T4, TSH. Tumor assessment at 16 weeks on Targretin® including self-reported pruritus questionnaire. Imaging with CT scans of the chest, abdomen and pelvis will be repeated at 16 weeks for stage IV patients if initial lymphadenopathy was present. Patients with Sézary syndrome will also have Sézary cell counts and/or flow cytometry repeated at 16 weeks. Responding patients may continue on Targretin® until progression. Followup visits will be at least every 3 months for 5 years or until signs or symptoms of tumor progression.

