Appendix 1: Patient Questionnaire

Patient Name _____

Study Site Name: _____

In this questionnaire, you will be asked about your itching and the use of anti-itching medications over the past week. Please complete this questionnaire before seeing your doctor.

(1) Overall, how badly has your skin itched over the past week? Please circle only one number.

0 1 2 3 4 5 6 7 8 9 10

No Itching

Itching as
bad as it
can be

(2) Overall, how has your use of prescribed or over the counter medications against itching, e.g., pills, creams, changed in the past week compared to the previous week? Please circle only one item.

- (A) I did not use any medications against itching in the past week
- (B) I used medication against itching in the past week, but the use is less than the previous week
- (C) I used medication against itching in the past week, but there is no change in the use
- (D) I used medication against itching in the past week, but the use is more than the previous week

Patient Signature: _____

Month _____ Day _____ Year _____

Study staff: This questionnaire must be completed, signed and dated by the patient before the patient is seen by the treating physician.

**Memorial Sloan-Kettering Cancer Center
IRB Protocol**

IRB#: 05-098 A(6)

**Appendix 2: Grading Scales for Composite Assessment (CA)
of Index Lesion Disease Severity**

Page 1 of 2

SCALING	0 - No evidence of scaling on the lesion 1* 2 - Mild: Mainly fine scales; lesion partially covered 3* 4 - Moderate: Somewhat coarser scales; lesion partially covered 5* 6 - Severe: Coarse, thick scales; virtually all of the lesion covered; rough surface 7* 8 - Very severe: Coarse, very thick scales; all of the lesion covered; very rough surface
ERYTHEMA	0 - No evidence of erythema, possible brown hyperpigmentation 1* 2 - Mild: Light red lesion 3* 4 - Moderate: Red lesion 5* 6 - Severe: Very red lesion 7* 8 - Very severe: Extremely red lesion
PLAQUE/TUMOR ELEVATION	0 - 0 mm: No evidence of plaque above normal skin level 1 - ≥ 0 to < 0.5 mm: Minimal but definite plaque elevation above normal skin level 2 - ≥ 0.5 to < 1 mm: Slight but definite plaque elevation 3 - ≥ 1 to < 1.5 mm: Mild elevation 4 - ≥ 1.5 to < 2 mm: Moderate elevation 5 - ≥ 2 to < 2.5 mm: Moderate to marked elevation 6 - ≥ 2.5 to < 3 mm: Marked elevation 7 - ≥ 3 to < 3.5 mm: Very marked elevation 8 - ≥ 3.5 mm: Extreme elevation

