Appendix 3: Schedule of Protocol Events																
Week	PreRx	W .2	W .4	W .6	W .8	W .10	W .12	W .14	W .14-16	W .14-16	W .16-18	W .18-20	W .22-24	W .26-28	W .30-32	
	Rx Dose 1	Dose 2	Dose 3	Dose 4	Dose 5	Dose 6	Dose 7	Dose 8		Rx Day 1	Rx W .2	Rx W .4	Rx W .8	Rx W .12	Rx W .16	
Resp. Eval.									X						X	
Rx	Do xil	Do xil	Do xil	Do xil	Do xil	Do xil	Do xil	Do xil		Targ retin	Targ retin	Targ retin	Targ retin	Targ retin	Targ retin	
Hx/Px	X	X	X	X	X	X	X	X	X	X	X	X	X	X	X	
KPS	X	X	X	X	X	X	X	X	X	X	X	X	X	X	X	
Toxicity assess.		X	X	X	X	X	X	X	X	X	X	X	X	X	X	
Tumor measurements	X								X***						X***	
Skin score																
Pruritus questionnaire	X								X						X	
CBC	X	X	X	X	X	X	X	X	X	X	X	X	X	X	X	
Fasting: Trigl.*** Cholest.	X								X		X	X	X	X	X	
Lytes, BUN, Cr., AST, ALT, alk. phos., bili., TP, alb., Ca, amylase, UA, gluc	X								X		X	X	X	X	X	
Urinal.	X															
T4, TSH	X								X		X	X	X	X	X	
Echo/MUGA	X															
CT c/a/p*	X								X						X	
Sézary cell CT/Flow	**** X								X						X	
beta-HCG**	X								X							
*Pts. with stage IV (TNM)																
**premenopausal women within 7 days																
***biopsy of residual lesions if CCR																
****fasting triglyc. obtained at each MD visit																
*****Pts. with Sézary syndrome																

Schedule of Protocol Events

**Memorial Sloan-Kettering Cancer Center
IRB Protocol**

IRB#: 05-098 A(6)

Appendix 4

DATA COLLECTION FORM SCHEDULE

FORM	BASELINE	CYCLE	OFFSTUDY	WHEN APPLICABLE
Demographic, Disease & Prior Treatment Form	X			
Comorbidity Form	X			
Original Pathology Reports*	X			
Original Radiology Reports	X			
Treatment & Treatment Modification Form		X	X	
Physical Exam Form		X	X	
Laboratory Form	X			
Toxicity Form		X	X	
Concomitant Drug Form	X	X	X	
Hospitalization Form				X
Patient Status & Outcome Form				X

* Pathology report must be faxed to the MSKCC Clinical Trials Office [contact] at the same time as patient registration that confirms patient has Cutaneous T-Cell Lymphoma.

Schedule:

Baseline: Forms to be submitted within two weeks of registration.

Cycle: To be completed after each cycle and submitted every 4 weeks.

Off-study: To be submitted within four weeks of the protocol completion.

Please submit forms to:

**[name], Research Study Assistant
Memorial Sloan-Kettering Cancer Center
[name]
[name]
[contact]**

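### Pruritus relief first seen at week 32 has no scheduled confirming questionnaire, and the rule does not say from when, or from which record, a medication increase is judged

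*Combined protocol and SAP*

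**What the plan says.** **Timing.** Section 12.7 (Pruritus Relief) fixes three time points: "The intensity of pruritus will be evaluated by the patient at baseline, at the week 16 (end of treatment with Doxil®) and week 32". Section 10.2 covers the form after Doxil: "Two item self-reported pruritus questionnaire will be administered at time of tumor assessment". Section 10.6 covers the form on Targretin: "Tumor assessment at 16 weeks on Targretin® including self-reported pruritus questionnaire". The row "Pruritus questionnaire" in Appendix 3 matches, with one mark before treatment, one at weeks 14-16 and one at weeks 30-32.

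**Rule.** The change required is "A 3-point decrease in pruritus intensity", which must be "confirmed by a second assessment at least 4 weeks later without an increase in the use of anti-pruritic medications". It is "considered clinically significant in those whose pruritus score is ≥ 3 on the 0-10 point scale at baseline".

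**Medication item.** Item 2 of the questionnaire in Appendix 1 asks how the use of anti-itch medication has "changed in the past week compared to the previous week".

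**Other contacts and records.** Section 12.5 sets an assessment 4 weeks after treatment ends, for response status and residual toxicity. Section 10.6 sets follow-up visits at least every 3 months. Neither mentions pruritus. Appendix 4 lists a Concomitant Drug Form at baseline, each cycle and off-study. The pruritus rule does not refer to it.

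**The concern.** A rule that needs two assessments needs a second assessment on the schedule for every time at which improvement can first be seen. Here that is so for week 16 but not for week 32. Section 3.0 gives as part of the rationale that Targretin may build on the initial response to Doxil. For itch, the written schedule could not register this in a patient who had no qualifying fall at week 16.

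The medication condition is there so that a lower score is not credited to study treatment when added anti-itch medication may explain it. The possibility is realistic: Section 6.1 allows topical corticosteroids below class 1 for T3 and T4 patients with intense pruritus. An item that looks back over two weeks cannot, alone, show whether use has risen since the start of the study.

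A reported pruritus-relief rate would therefore omit some relief that first appears on Targretin, and might include some relief that added medication could explain.

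**Working it through.** The plan gives no numerical claim for pruritus, so there is no figure to reproduce. The check sets the schedule against the rule.

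**Inputs.** Questionnaire times: nominal weeks 0, 16 and 32 (Section 12.7), with windows of weeks 14-16 and 30-32 (Appendix 3). Minimum confirmation interval: 4 weeks (Section 12.7). Start of Targretin: within 2 weeks after the tumor assessment (Section 10.5). Span of item 2: the past week plus the week before, 2 weeks in all (Appendix 1).

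**Step 1. Can a first improvement be confirmed?** The interval is the time of the next scheduled form minus the time of first improvement.

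| First seen | Next scheduled form | Interval | At least 4 weeks? |
|---|---|---|---|
| Week 16 | Week 32 | 32 − 16 = 16 weeks | Yes |
| Week 32 | None | Not defined | No |

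Taking the two Appendix 3 windows as independent, the first interval runs from 30 − 16 = 14 to 32 − 14 = 18 weeks. Every value exceeds 4.

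**Step 2. What does the long interval imply for week-16 relief?** Relief that lasts 4 to 12 weeks and then fades meets the 4-week idea but is not recorded as confirmed, because the next form comes about 16 weeks later. The same applies to a patient who leaves between weeks 16 and 32 for progression or unacceptable toxicity (Section 13.0): no confirming form is scheduled for that patient.

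**Step 3. How much time does item 2 cover?** The week-16 answer covers weeks 14 to 16, which leaves 16 − 2 = 14 weeks since baseline uncovered. The week-16 and week-32 answers together cover 2 + 2 = 4 of 32 weeks and leave 32 − 4 = 28 uncovered. A patient who raised use at week 6 and held it steady would truthfully report no change at week 16.

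**Step 4. What does item 2 still tell us?** Answer (A), no use in the past week, excludes an increase at that time. A move from (A) at baseline to any other answer later shows that use has begun. The gap concerns patients who report use at both times.

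**Step 5. Would extra forms close the gap in Step 1?** Targretin starts 0 to 2 weeks after the post-Doxil assessment, so the Targretin week-4 visit falls 4 to 6 weeks after it and can confirm week-16 relief. Relief first seen at Targretin week 12 can be confirmed at Targretin week 16, since 16 − 12 = 4 weeks, which is exactly the minimum. Relief first seen at week 32 still needs a form at week 36 or later.

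**The case against.** **The rule works for week 16.** A reader might infer that the rule cannot operate on its schedule, or that 16 weeks breaches a 4-week requirement. Neither follows. Four weeks is a floor, and 16 weeks is a stricter test of persistence. This objection stands in full.

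**Confirmatory visits need not appear in Appendix 3.** Section 12.7 also asks for progression to be confirmed 1-4 weeks later and for partial response to be maintained for 4 weeks, and neither has its own row. A site could likewise repeat the questionnaire at a later visit. It would therefore be too strong to say that week-32 relief can never be confirmed. What remains is that no provision calls for the form after week 32, so confirmation would depend on each site's initiative.

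**Medication use is recorded elsewhere.** A reader might infer that increases between questionnaires go unrecorded. The Concomitant Drug Form and the history taken at visits speak against that. Nor does the rule say that an increase is counted from baseline. That reading is an inference, though a natural one, because the score threshold for the rule refers to baseline. What stands is narrower: the rule leaves both the reference time and the source open.

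**Attribution to one drug is not an objective.** Section 2.0 concerns the two drugs in sequence. Confirming week-16 relief after 16 weeks of Targretin limits what can be said of Doxil alone, but contradicts no stated aim.

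**Little depends on this outcome.** Pruritus is absent from the objectives in Section 2.0 and the endpoints in Section 14.0, and raw scores at all three times remain reportable. This is correct and limits the weight of the point.

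**Conclusion.** The point holds in limited form. On the written schedule, relief at week 16 can be confirmed only if it persists for about 16 weeks into Targretin, and relief first seen at week 32 has no scheduled confirming questionnaire. Item 2 alone would miss a medication increase made earlier and then held steady. The rule defines neither the reference time for an increase nor the record that decides it.

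The effect on a reported relief rate cannot be sized, because the documents give no expected frequency of relief at either time or of changes in anti-itch medication. The conclusion assumes that Sections 10.2, 10.6 and 12.7 and Appendix 3 list every planned questionnaire, and that an increase is meant relative to baseline. It does not touch the primary endpoint, the sample size of 37 or the threshold of 24 progression-free patients. It is a modest improvement to a supporting outcome.

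**What to change.** 1. Give the two-item form also at the existing Targretin week-4 and/or week-12 visits. Week 4 offers an earlier confirmation of week-16 relief. Week 12 lets relief that appears on Targretin be confirmed at week 32. Because both intervals can be exactly 4 weeks, the visit windows should not let the second form fall early.
2. Give it once more at the first follow-up visit at least 4 weeks after week 32: a Section 10.6 visit for patients who continue Targretin, and the Section 12.5 assessment for those who have stopped. The Section 12.5 assessment alone would not do, because for responders who stay on Targretin until relapse it may come only after relapse.
3. Define an increase in anti-pruritic medication as compared with baseline, with the Concomitant Drug Form as the source and item 2 as support. The protocol counts cycles only for Doxil, so it should state that this form is also completed at the Targretin visits that carry the questionnaire. Its content is not shown, so check that it records the amount of anti-itch medication used. Rewording item 2 to ask about use before study treatment is less suitable: it would need recall over up to 32 weeks and has no sensible answer at baseline.

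The cost is two questions at visits already planned, with slight patient and data-entry burden.
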